1.3 Schedule of Activities

If the COVID-19 pandemic prevents participants from coming to the site, participants can have their study visit assessments performed remotely as judged appropriate by the investigator. This must be discussed with the sponsor before being implemented. In such a case, the investigator will perform a telemedicine visit and will make every effort, where applicable, to contact the participant's general practitioner or specialist physician to ensure all important medical information and safety event(s) occurring since the last visit are collected. Guidance on how to collect protocol-planned assessments will be provided to the investigator in a separate document. Such document will be filed in the trial master file. Independent ethics committees (IECs)/institutional review boards (IRBs) will be notified of the changes as applicable locally. Of note, as the adapted visit deviates from the regular protocol plan, the changes will be recorded as protocol deviations related to COVID-19.

Table 2 Schedule of Activities

Procedures [a]	Screening Visit		Month 3	Month 6	Month 9	Month 12
	Day -28 to Day -1 Prior to Treatment	Day 1	Day 85	Day 169	Day 253	Day 337 (EOS/Early Withdrawal) [u]
Visit window (days)			±3 days	±3 days	±3 days	+7 days
Informed consent /assent [b]	X					
Inclusion and exclusion criteria [c, d]	X	X				
Demography	X					
Medical and surgical history	X					
PK samples[e]		X	X	X		X
Basal LH and FSH [f]	X		X	X	X	X
GnRH test with LH and FSH [g]	X		X	X		X
Oestradiol or testosterone [h]	X		X	X	X	X
Pubertal Stage (Tanner method) [i]	X			X		X
Auxological parameters [j]	X		X	X	X[v]	X
Bone age [k] and chronological age	X			X		X
Gonad development [l]	X			X		X
Body weight [m]	X	X	X	X	X	X
Adverse events [n]	X	X	X	X	X	X
Pregnancy test [o]		X				X
Clinical laboratory tests [p]	X	X[w]	X	X	X	X
Physical examination and vital signs [q]	X	X	X	X	X	X

CONFIDENTIAL

PROTOCOL VERSION 2.0: 29 APRIL 2022

PAGE 20/63

Procedures [a]	Screening Visit		Month 3	Month 6	Month 9	Month 12
Prior and concomitant medications [r]	X	X	X	X	X	X
Study drug administration [s]		X		X		
Local tolerability [t]		X		X		

BMI=body mass index; CPP=central precocious puberty, eCRF=electronic case report form, EOS=End of Study; FSH=follicle-stimulating hormone; GnRH=gonadotropin-releasing hormone; IEC=Independent Ethics Committee; IRB=Institutional Review Board; LH=luteinising hormone; MRI=magnetic resonance imaging, PK=pharmacokinetic.

Footnotes to Schedule of Assessments

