- a **Study procedures** to be done before dosing except local tolerability and post-dose PK. Note that in the case that Screening is more than 1 week prior to first intervention, clinical laboratory tests (chemistry, haematology and urinalysis) will need to be reassessed.
- b **Informed consent/assent** to be performed by parent/legal guardian and by children if determined by local IRB/IEC requirements.
- c **Eligibility check** of inclusion and exclusion criteria to occur at Screening and prior to dosing on Day 1.
- d **Head (Pituitary) MRI** for all subjects to confirm CPP and check for tumours at screening, unless they have available MRI scans within 6 months for site to verify.
- e **PK Samples** on Day 1 to be taken predose and at 4 hours postinjection (± 2 -hour window); PK sample at Month 3 visit, Month 6 (predose of second injection, and 4 hours postinjection (± 2 hour window)), and Month 12 EOS/early withdrawal visits to be taken preGnRH agonist stimulation.
- f **Basal LH and FSH** samples to be drawn before GnRH test. Blood sampling should be taken at approximately the same time of day during each visit.
- g **GnRH test** samples for LH and FSH concentrations will be collected at 30, 60 and 90 minutes after the GnRH test.
- h **Oestradiol and Testosterone** samples for girls and boys, respectively. Blood sampling should be taken at approximately the same time of day during each visit.
- i **Tanner pubertal stage** as defined in [Appendix 6](#).
- j **Auxological parameters** including height, growth velocity, BMI will be assessed.
- k **Bone Age** by Greulich and Pyle method.
- l **Gonad development** uterine length in girls assessed by Type B ultrasound or testicular volume in boys assessed by orchidometer.
- m **Body weight** is required for administration of gonadorelin in the GnRH test.
- n **Adverse events** will be collected up to and including the Month 12 visit (i.e. Day 337+7 days).
- o **Pregnancy test** for female participants only. Girls who have entered menarche must have a negative pregnancy test prior to the start of study treatment and should not be at risk of pregnancy throughout the study period. Local urine testing will be standard for the protocol unless serum testing is required by local regulation or IRB/IEC before drug treatment for all female participants of childbearing potential and if clinically indicated thereafter. First pregnancy test to be performed within 24 hours prior to first injection.

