2.2 Background

Precocious puberty is a condition that causes early sexual development in girls and boys. While the chronological age (CA) limit for the onset of puberty is 8 years in girls and 9 years in boys for children in North America and Western European countries [\[Carel 2008\]](#), children with precocious puberty exhibit precocious pubertal development that can be 2.5 to 3 SDs earlier than the current estimated average. The prevalence of precocious puberty is 10 times higher in girls than in boys [\[Carel 2008\]](#).

In a minority of children, precocious puberty can occur due to an organic lesion (cerebral tumour); in most children, this condition is caused by the early release of GnRH (also known as luteinising hormone-releasing hormone (LHRH)) by the hypothalamus. In healthy children, GnRH stimulates the release of pituitary gonadotropins follicle-stimulating hormone (FSH) and LH, which is then followed by prolonged suppression of these hormones, contributing to normal pubertal development. The form of precocious puberty caused by early GnRH stimulation is termed CPP. In children with CPP, early GnRH release leads to the precocious secretion of LH and FSH which, in turn, activate the early secretion of gonadal hormones by the ovaries or testes.

Signs of puberty include pubic and axillary hair growth and changes in the child's body shape and behaviour. Boys develop facial hair and their penis lengthens and girls develop breasts and may have menstrual periods. In children with CPP, these signs prematurely appear before the age of 8 years in girls and 9 years in boys, respectively. Furthermore, growth velocity accelerates, initially inducing a rapid height increase, which stops at an early age. Accelerated bone maturation leads to premature epiphyseal closure and a final height below the target height that was otherwise expected for the child's age. These premature changes may also lead to psychological disorders in children with CPP.

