8.2.1 Physical Examinations

- A complete physical examination will include, at a minimum, assessments of the cardiovascular, respiratory, gastrointestinal and neurological systems. Height and weight will also be measured and recorded. Body weight will be measured in underwear and without shoes.
- A brief physical examination will include, at a minimum, assessments of the skin, lungs, cardiovascular system, and abdomen (liver and spleen).
- Investigators should pay special attention to clinical signs related to previous serious illnesses.
- Any clinically significant physical examination findings (abnormalities) observed during the study will be reported as AEs. Any physical examination findings (abnormalities) persisting at the end of the study will be followed by the Investigator until resolution or until reaching a clinically stable endpoint.

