5.1.2 Descriptive Statistics

All raw and derived variables will be listed and described using summary statistics. For categorical variables, summary statistics will be displayed using descriptive statistics by frequency count and percentages by category. The missing category will be presented if there is at least one missing category for at least one gender group. Except otherwise specified, participants with missing data will be included in the calculation of percentages. For quantitative variables, summary statistics will be displayed using descriptive statistics by number of observations, mean, SD, median, minimum and maximum. Missing data will be displayed.

5.1.3 *Baseline Value*

Unless otherwise specified, baseline is defined as the last non-missing measurement taken prior to first IMP administration (including unscheduled assessments). If the assessment time and/or IMP administration time is not collected, the assessment performed on the same day as the first IMP administration will be considered as baseline.

5.1.4 *Reference Start Date and Study Day*

Reference start date is defined as the day of the first IMP administration.

The day of the first IMP administration will be Day 1. Study day will be calculated as:

- The difference between the event date and the reference date plus one day, if the event is on or after the reference date.
- The difference between the event date and the reference date, if the date of event is prior to the reference date.

Study day will appear in any listings where an assessment date or event date appears.

In case of partial or missing event date, study day will appear missing while any associated durations will be presented based on the imputations described in appendix A2.

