5.7.3 Analysis of Secondary Efficacy Endpoints

5.7.3.1 Endpoint

Secondary efficacy endpoints and evaluations are summarised in following table:

Table 1 Secondary Efficacy Endpoints and Evaluations

| Measure | Timepoint | Variable | Endpoint |
|--|--|--|---|
| Peak LH after GnRH stimulation test | Month 3 and Month 12 | LH suppression (stimulated peak LH ≤ 5 IU/L after GnRH stimulation) | 
 Proportion of children with LH suppression defined as stimulated peak LH ≤ 5 IU/L after GnRH stimulation at Month 3 and 12 |
| | Month 6 and Month 12 | | 
 Proportion of children maintaining LH suppression defined as stimulated peak LH ≤ 5 IU/L after GnRH stimulation from Month 6 to 12 |
| Basal LH and FSH | Baseline, Month 3, Month 6, Month 9 and Month 12 | LH and FSH concentration | Change in basal serum LH and FSH levels at Months 3, 6, 9 and 12 compared to baseline |
| Peak LH and FSH after GnRH stimulation test | Baseline, Month 3, Month 6 and Month 12 | LH and FSH concentration | Change in peak serum LH and FSH levels at Months 3, 6 and 12 compared to baseline |
| Pre-pubertal levels of sex steroids | Month 3, Month 6, Month 9 and Month 12 | oestradiol ≤ 20 pg/mL [<73 pmol/L] in girls or testosterone ≤ 30 ng/dL [<0.8 nmol/L] in boys | 
 Proportion of children with pre-pubertal levels of sex steroids (defined as oestradiol ≤ 20 pg/mL in girls or testosterone ≤ 30 ng/dL in boys) at Months 3, 6, 9 and 12 |
| | Baseline, Month 3, Month 6, Month 9 and Month 12 | | 
 Change in sex steroids levels at Months 3, 6, 9 and 12 compared to baseline |
| Height (Z-score and percentile for height for age) and growth velocity | Baseline, Month 6, and Month 12 | Height (Z-score and percentile for height for age) and growth velocity | 
 Change in height (Z-score [height for age] and percentile for height for age) and growth velocity at Months 6 and 12 Height absolute Z-scores and percentiles at Baseline, Months 6, and 12 Change in Height at Months 6, and 12 compared to baseline |

| | | | |
|--|--|---|---|
| BA (Greulich and Pyle method):CA ratio | Month 6 and Month 12 | BA and CA | Proportion of children in whom the BA (Greulich and Pyle method):CA ratio did not rise at Months 6 and 12 relative to baseline (X-ray) |

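### Day 1 height is left undefined: followed as scheduled, weight has a Day 1 baseline but height and BMI have a Screening baseline up to 28 days older

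*Protocol*

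**What the plan says.** **Schedule.** In Protocol section 1.3, Table 2, the row "Auxological parameters [j"] is marked at Screening and at Months 3, 6, 9 and 12, and its Day 1 cell is empty. Footnote j defines the content of that row: "including height, growth velocity, BMI will be assessed". Body weight is marked at every visit, including Day 1. The Screening column runs "Day -28 to Day -1 Prior to Treatment".

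**Physical examination.** The row "Physical examination and vital signs [q"] is marked at every visit, including Day 1. Protocol section 8.2.1 describes two kinds of examination. For the complete one it says "Height and weight will also be measured and recorded". The brief one has a minimum content that does not list height. Neither Table 2 nor footnote q says which kind applies on Day 1.

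**Baseline.** SAP section 5.1.3 states that "baseline is defined as the last non-missing measurement taken prior to first IMP administration (including unscheduled assessments"). Footnote a to Table 2 places study procedures before dosing, apart from local tolerability and the post-dose PK samples. A height taken on Day 1 would therefore qualify as baseline.

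**Endpoints.** The protocol's height endpoints are change in height Z-score, change in percentile, and growth velocity, at Months 6 and 12. SAP Table 1 (section 5.7.3.1) adds "Change in Height at Months 6, and 12 compared to baseline", that is, the change in cm. SAP section 7 derives BMI from the weight and height measured at each visit. SAP Appendix A5 interpolates the height reference values to the child's actual age.

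**The concern.** Height rises every day, and Protocol section 2.2 says that in untreated disease "growth velocity accelerates, initially inducing a rapid height increase". If baseline height is the Screening value, the change reported at Month 6 covers the time on treatment plus an untreated stretch whose length differs from child to child. A single-arm study has no control group in which this would cancel.

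There are two further consequences. Weight and BMI share one endpoint row but would have baselines on different dates. And if some sites perform a complete examination on Day 1 while others perform a brief one, the same height table would mix Day 1 and Screening baselines without saying so.

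The protocol already treats some screening data as ageing: under footnote a, safety laboratory tests more than one week old are repeated before the first dose. Height has no such rule.

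**Working it through.** The documents give no growth velocity and no expected height change, so there is no figure of the plan's own to reproduce here. The day counts come from the documents; the velocities are assumptions.

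**Inputs from the documents**
- Largest gap from Screening to first dose: 28 days (Table 2).
- Month 6 is Day 169, so 169 - 1 = 168 days after the first dose. Month 12 is Day 337, so 336 days.

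**Assumed inputs**
- Untreated velocity v0 = 7 to 11 cm/year; treated velocity v1 = 4.5 to 6.5 cm/year.
- For Z-score only: v0 = 6 to 11 cm/year, reference velocity 5.5 to 6 cm/year, height SD 5.5 to 6.5 cm.

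**Step 1: change in height in cm**
- Untreated increment = v0 x gap/365.25. For 28 days: 7 x 28/365.25 = 0.54 cm, up to 11 x 28/365.25 = 0.84 cm.
- True on-treatment change at Month 6 = v1 x 168/365.25 = 2.07 to 2.99 cm.
- Inflation relative to the on-treatment change = (v0/v1) x gap/168 at Month 6, or (v0/v1) x gap/336 at Month 12.
- Floor, requiring only v0 >= v1: 28/168 = 16.7% and 28/336 = 8.3%.
- Range at 28 days, Month 6: (7/6.5) x 28/168 = 18%, up to (11/4.5) x 28/168 = 41%. Month 12: half of these, 9% to 20%.

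| Gap (days) | Month 6 floor | Month 6 range | Month 12 floor | Month 12 range |
|---|---|---|---|---|
| 28 | 16.7% | 18-41% | 8.3% | 9-20% |
| 14 | 8.3% | 9-20% | 4.2% | 4.5-10% |
| 7 | 4.2% | 4.5-10% | 2.1% | 2.2-5.1% |

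**Step 2: height Z-score and percentile**
- Both are computed at actual age, so only growth in excess of the reference carries over: (v0 - reference) x 28/365.25 / SD.
- Smallest: (6 - 6) x 28/365.25 / 6.5 = 0.00 SD. Largest: (11 - 5.5) x 28/365.25 / 5.5 = 0.08 SD.
- Near the median, 0.08 SD is about 0.08 x 0.399 = 0.03, or 3 percentile points.

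**Step 3: growth velocity**
- SAP section 7 says only how to handle a velocity recorded as a range. It gives no interval and no annualising formula.
- If the Screening height is used and actual dates are the divisor, the excess at Month 6 is (v0 - v1) x 28/196: from 0.5 x 28/196 = 0.07 to 6.5 x 28/196 = 0.93 cm/year.
- If the nominal 168 days is the divisor, the excess is v0 x 28/168: from 1.17 to 1.83 cm/year.
- A velocity taken between two visits after Day 1 is not affected.

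**Step 4: BMI**
- With no Day 1 height there is no Day 1 BMI, so baseline BMI is the Screening value while baseline weight is the Day 1 value.

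**The case against.** A reader might infer that height is not measured on Day 1 and that baseline height is therefore always the Screening value. The documents do not establish this. An examination is scheduled on Day 1, a complete one records height, and the SAP rule would adopt that height as baseline. What the documents show is that Day 1 height is undefined between Table 2 and section 8.2.1.

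A reader might also carry the upper figure of 41% over to every height endpoint. It applies only to the change in cm, which appears in the SAP but not among the protocol's endpoints. It combines the fastest assumed untreated growth, the slowest assumed treated growth and the maximum gap, and it supposes that velocity changes at the moment of injection. Z-score and percentile are largely protected by the adjustment to actual age. The documents say nothing about typical screening length.

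Nor is baseline BMI a mixture of a Day 1 weight and a Screening height: the SAP derives BMI from values measured at each visit.

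The other points against the concern are fair:
- Extra pre-dose growth makes growth on treatment look faster, so it cannot flatter the drug.
- The summaries are descriptive and no test depends on them.
- Hormones, Tanner stage, bone age and gonad size also have Screening as their only scheduled pre-dose visit, and a Screening height matches the bone-age baseline.
- SAP sections 5.1.4 and 5.7.1 already put study day in the efficacy listings, so the gap can be read child by child.

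These points limit the importance of the finding. They do not settle which height is the baseline, and a listing does not show a reader of the height-change table how much untreated time it contains.

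**Conclusion.** The point holds as a minor one. Table 2 and section 8.2.1 leave Day 1 height undefined. Followed as scheduled, the plan gives weight a Day 1 baseline and gives height and BMI a Screening baseline up to 28 days older; if practice differs between sites, the height baselines are mixed.

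Where the Screening height is the baseline, the change in height in cm is inflated. At the maximum gap the inflation is at least 16.7% at Month 6 and 8.3% at Month 12, which rests only on untreated growth being no slower than treated growth. The ranges of 18-41% and 9-20% rest on assumed velocities. The Z-score effect is about 0.00-0.08 SD, also on assumed values, and the effect on growth velocity depends on an interval the SAP does not state.

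Only descriptive secondary summaries are affected, in a direction unfavourable to the drug. The primary LH endpoint and its sample size do not use height and are unchanged.

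**What to change.** - In Table 2, mark height on Day 1, before dosing, alongside the weight already scheduled there. Reconcile this with section 8.2.1 by stating whether the Day 1 examination is complete or brief.
- The SAP baseline rule needs no change. With a Day 1 height it gives height, Z-score, percentile, weight and BMI the same baseline date, and the height interval becomes 168 days at Month 6 and 336 days at Month 12, instead of up to 196 and 364.
- For children already dosed without a Day 1 height, summarise the days from baseline height to Day 1 with the height-change table.
- State in the SAP which two heights and which dates define growth velocity.

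The cost is one height measurement at a visit where the child is already weighed and examined, one mark in Table 2, and one extra summary line. For children already dosed, the untreated interval can be reported but not removed.

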**D-CN-52014-244****CONFIDENTIAL****PROTOCOL VERSION 2.0: 29 APRIL 2022****PAGE 21/63**

1.4 Brief Summary

The purpose of this study is to assess the safety and efficacy of the triptorelin 6-month formulation in Chinese children with CPP. Efficacy will be defined by peak (LH levels ≤ 5 IU/L) after i.v. GnRH stimulation at Month 6.

Study Participant Duration: approximately 13 months; i.e. screening and two injections of the study intervention.

Intervention Duration: approximately 12 months; i.e. two injections of the study intervention.

Visit Frequency: Screening, Day 1, Months 3, 6, 9 and 12.

Approved

2 INTRODUCTION

Triptorelin is an agonist analogue of natural GnRH. The principal modification consists of substitution of natural glycine in position 6 by a D-amino acid (D tryptophan). Clinical and animal studies have provided positive results of triptorelin's action in hormone-dependent disorders such as CPP, prostate cancer, endometriosis, uterine fibromyomas, in vitro fertilisation and breast cancer.

2.1 Study Rationale

Currently marketed in China there is a triptorelin 1-month formulation indicated for the treatment of children with CPP.

A global pivotal study, DEBIO 8206-CPP-301, demonstrated the efficacy and safety of the 6-month formulation over a period of 12 months and led to registration in the EU and USA.

This current study is intended to document the efficacy, safety and PK of triptorelin 6-month formulation in Chinese children with CPP over a period of 12 months.

Henceforth in this protocol, triptorelin pamoate 22.5 mg 6-month formulation will be referred to as 'triptorelin 6-month formulation'.

2.2 Background

Precocious puberty is a condition that causes early sexual development in girls and boys. While the chronological age (CA) limit for the onset of puberty is 8 years in girls and 9 years in boys for children in North America and Western European countries [\[Carel 2008\]](#), children with precocious puberty exhibit precocious pubertal development that can be 2.5 to 3 SDs earlier than the current estimated average. The prevalence of precocious puberty is 10 times higher in girls than in boys [\[Carel 2008\]](#).

In a minority of children, precocious puberty can occur due to an organic lesion (cerebral tumour); in most children, this condition is caused by the early release of GnRH (also known as luteinising hormone-releasing hormone (LHRH)) by the hypothalamus. In healthy children, GnRH stimulates the release of pituitary gonadotropins follicle-stimulating hormone (FSH) and LH, which is then followed by prolonged suppression of these hormones, contributing to normal pubertal development. The form of precocious puberty caused by early GnRH stimulation is termed CPP. In children with CPP, early GnRH release leads to the precocious secretion of LH and FSH which, in turn, activate the early secretion of gonadal hormones by the ovaries or testes.

Signs of puberty include pubic and axillary hair growth and changes in the child's body shape and behaviour. Boys develop facial hair and their penis lengthens and girls develop breasts and may have menstrual periods. In children with CPP, these signs prematurely appear before the age of 8 years in girls and 9 years in boys, respectively. Furthermore, growth velocity accelerates, initially inducing a rapid height increase, which stops at an early age. Accelerated bone maturation leads to premature epiphyseal closure and a final height below the target height that was otherwise expected for the child's age. These premature changes may also lead to psychological disorders in children with CPP.

There is currently no nationwide epidemiology study of CPP data in China. Only two studies have been published about the incidence of precocious puberty in two cities: Jiu Jiang (study with 3,312 children investigated and an incidence of 0.68%, 1.25% in girls and 0.11% in boys) [\[Hu 2012\]](#) and Zhengzhou (study with 8,750 children investigated and an incidence of 0.74%, 1.37% in girls and 0.26% in boys) [\[Wei 2010\]](#). In coastal areas of China, precocious puberty has an incidence rate of 0.38%; the incidence in girls is higher at 0.67%. The prevalence of

precocious puberty in Shanghai is 100/10,000 [[Lin 2004](#)]. These data refer to precocious puberty without GnRH-dependent stimulation, which is not specific for CPP and are probably lower than numbers described above.

As reported by Carel and Léger [[Carel 2008](#)], the assessment of gonadotropin levels (based on ultrasensitive assays) is central to the diagnosis of CPP. The gold standard for evaluation is the measurement of gonadotropin levels after stimulation with GnRH or a GnRH agonist (GnRHa). Peak LH levels of 5 to 8 IU/L suggest progressive CPP but there is an overlap between prepubertal and early pubertal values [[Carel 2008, Resende 2007](#)]. Caution should be taken when interpreting gonadotropin levels in children younger than 2 to 3 years old as gonadotropin levels are normally high in this age group [[Carel 2008](#)].

In CPP (i.e. with no other identified cause such as a cerebral tumour), there is no surgical therapy available and no effective alternative therapeutic option other than taking a prolonged release (PR) formulation of synthetic GnRH. In severe cases, untreated CPP causes physical and psychological problems for the child.

Treatment with GnRH analogues, which act by downregulating pituitary GnRH receptors [[Carel 2009, Comite 1981 Crowley 1981, Bertelloni 2013](#)] represent the standard of care for the treatment of CPP [[Carel 2009](#)]. Their efficacy to stop precocious development has been demonstrated and their use involves only minor adverse events (AEs). A review of CPP treatment by Krishna et al confirmed that treatment with PR formulations of GnRHAs is safe, with relatively minor side effects, and supported that the outcome in terms of final height is favourable in most patients [[Krishna 2019](#)].

Diphereline® (international non-proprietary name (INN): triptorelin) is a synthetic GnRH analogue that is mainly characterised by the replacement of the L-glycine in the 6th position by a D-tryptophan. This structural modification increases both the resistance to enzymatic degradation and the affinity to the pituitary receptor, thus prolonging the plasma half-life ($t_{1/2}$) and increasing the potency of the drug.

In China, Diphereline® is available as a 1-month formulation, which is approved for use in patients with CPP, prostate cancer and metriosis, fibromyomas and female infertility.

Study DEBIO 8206-CPP-301 was the first 6-month triptorelin clinical trial in the treatment of CPP sponsored by Debiopharm International SA [[Klein 2016](#)]. This was an international, multicentre, nonrandomised, open-label, noncomparative phase III study of two i.m. injections of triptorelin 6-month formulation administered twice over 12 months in a group of 44 children with CPP comprising 39 girls and 5 boys. The 6-month formulation was safe and effective in suppressing the pituitary-gonadal axis in children with CPP. The extended injection interval may improve compliance and increase comfort in the management of CPP.

The worldwide marketing status of all triptorelin formulations of which Ipsen and Debiopharm are the marketing authorisation holders (marketed by Ipsen under Debiopharm/Ipsen agreement) can be found in the Investigator's Brochure (IB). Further details/additional information regarding risks and benefits to participants may also be found in the IB.

A more detailed description of the product, including further details on administration procedures and dosage are provided in Section 6.

